10.2 Subgroup Analyses

If ≥ 5 Japanese subjects are enrolled to the study, the following subgroup analysis will be carried out for Japanese and all subjects:

- Descriptive analysis of the primary endpoint: time-normalized number of HAE attacks per month during the Treatment Period, see [Section 10.1](#);
- Descriptive analysis of the reduction in attack rate during the Treatment Period, see [Section 10.3.2.1](#);
- Descriptive analysis of time-normalized number of HAE attacks requiring on-demand treatment, see [Section 10.3.2.2](#);
- Overview summary of TEAEs, see [Section 11.2](#);

If ≥ 5 Japanese subjects are enrolled to the study, the following subgroup analysis will be carried out for Japanese/non-Japanese subjects:

- Summary for CSL312 concentrations, see [Section 12.1](#).

Summaries for CSL312 concentrations will further be stratified by Age group (adolescent [12 to ≤ 17 years] and adult [>17 years] subjects), see [Section 12.1](#).

10.3 Analysis of Secondary Endpoints

Efficacy secondary endpoints are:

- The reduction in the attack rate during the Treatment Period compared to the Run-in Period,
- The time-normalized number of HAE attacks requiring on-demand treatment,
- The time-normalized number of moderate and / or severe HAE attacks,
- Time-normalized number of HAE attacks at various time points during the treatment period,
- **CCI**

Safety secondary endpoints are:

- AEs,
- AESIs,
- SAEs,
- CSL312 induced anti-CSL312 antibodies,
- Clinically significant abnormalities in laboratory assessments (ie, laboratory abnormalities reported as AEs).

10.3.1 Secondary Estimand

No secondary estimand is defined.

10.3.2 Secondary Efficacy Analysis

Secondary efficacy endpoints will be analyzed for ITT Analysis Set.

10.3.2.1 The Reduction in the Attack Rate during the Treatment Period compared to the Run-in Period

The secondary efficacy endpoint of the percentage reduction in the time-normalized number of HAE attacks is calculated within a subject as:

$$100 * [1 - (\text{time-normalized number of HAE attacks per month during Treatment Period} / \text{time-normalized number of HAE attacks per month during Run-in Period})]$$

with time-normalized number of HAE attacks per month during Treatment Period as defined in [Section 10.1](#) and with time-normalized number of HAE attacks per month during Run-in Period defined as:

$$[\text{the number of HAE attacks during Run-in Period} / \text{length Run-in Period in days}] * 30.4375$$

where the length of subject's Run-in Period is calculated as:

[Day 1 Visit date of the Treatment Period or Date of Run-in Completion/Non-completion [whichever is first] – Day 1 Visit date of Run-in Period]

for the entire 6-months Treatment Period and will be summarized and tested via a two-sided Wilcoxon Test with alpha = 5%.

The number and percentage of responders and non-responders will be presented with corresponding 95% CIs. A subject is classified as a responder if the percentage reduction in time-normalized HAE attacks is $\geq 50\%$. In addition, the number and percentage of subjects with percentage reductions of $\geq 70\%$, and $\geq 90\%$ will be presented with corresponding 95% CIs.

The number and percentage of subjects with a percentage reduction of 100%, ie, who do not experience a HAE attack and so are attack-free, will be presented and summarized with corresponding 95% CI for the 6-month Treatment Period, a Fisher-Test will be performed to assess for differences between treatment arms.

The number and percentage of subjects who do not experience a HAE attack in the first 3 months after first study drug administration and so are attack-free will be presented and summarized with corresponding 95% CIs. A Fisher-Test will be performed to assess for differences between treatment arms (Hierarchical Testing H03).

The same analysis will be repeated for the second 3 months after first study drug administration.

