4.1.3 Criteria for Entry into the Treatment Period

Subjects will be eligible to exit the Run-in Period and enter the Treatment Period if they meet all the following criteria:

1. Participated in the Run-in Period for at least 1 month.
2. Experienced at least an average of 1 HAE attack per month during the Run-in Period (eg, experienced a total of at least 2 HAE attacks).
3. Does not have laboratory clinical abnormalities assessed as clinically significant by the investigator in results of hematology, chemistry, or urinalysis assessments.
4. C1-INH functional activity and antigen, and C4 antigen concentration levels have been verified prior to randomization.

Note: Subjects with \geq 2 times the upper limit of normal for aspartate aminotransferase and / or alanine aminotransferase may be eligible for participation if there is an explanation for this laboratory result and if the results are not clinically significant.

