8.7.3.3 Run-in Period: Day 60 ± 4 days

The following procedures will be conducted at Visit Day 60 during the Run-in Period:

- Telephone contact for all subjects.
- eDiary completion by subject.

- Review of eDiary data.
- Close eDiary access (only applicable for subjects not eligible to enter the Treatment Period).
- Confirm access to on-demand HAE medication.
- Record concomitant medications and therapies (type, dose, route, date, and time).
- Record AEs.

Subjects should enter the Treatment Period no later than 15 days after the Day 60 telephone contact. If a subject is unable to enter the Treatment Period within the 15 days after the Day 60 telephone contact, then CSL approval is required for the subject to enter the Treatment Period. The Day 60 telephone contact will conclude the Run-in Period for a subject who has entered the Run-in Period and is subsequently not eligible to be assigned to treatment with investigational product in the Treatment Period.

Subjects who enter the Run-in Period but are not eligible to enter the Treatment Period will be considered Run-in failures. If a subject is not eligible to enter the Treatment Period, the primary reason for Run-in failure must be documented. These subjects may not be rescreened.

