8.3 Study Periods relative to Treatment

The following definitions for the periods of efficacy and safety will be used to define the durations used in the denominator of the time-normalized endpoints and safety endpoints such as exposure and subject-years.

Table 8 Overview Study Periods

Study Period	Start Date	End Date	Duration
Screening Period	date of Informed Consent	date/day on which eligibility for Run-in Period was confirmed	Day 1 Visit date of Run-in Period – date of Informed Consent
Run-in Period	date/day on which eligibility for Run-in Period was confirmed	date of the Day 1 Visit of Treatment Period	Day 1 Visit date of the Treatment Period or Date of Run-in Completion/Non-completion [whichever is first] – Day 1 Visit date of Run-in Period

Study Period	Start Date	End Date	Duration
Treatment Period/ Efficacy Evaluation Period	date of the Day 1 Visit of Treatment Period	date of the Day 182 Visit of the Treatment Period or the End of Study date for subjects who prematurely discontinued [whichever occurs earlier]	Day 182 Visit date of the Treatment Period or End of Study date [whichever is first] – Day 1 Visit date of the Treatment Period + 1
Follow-up Period	date of the Day 182 Visit of the Treatment Period	date of the Follow-up/Final Visit (Day 242 Visit)	date of the Follow-up/Final Visit (Day 242 Visit) – date of the Day 182 Visit of Treatment Period
Safety Period	date and time of the first administration of investigational product	Date of End of Study	Date of End of Study - date of the first administration of investigational product

Technical Notes:

- Screening Period: The first day of the Run-in Period may occur on the same day as the Screening Visit for subjects meeting the eligibility criteria for the Run-in Period. Those subjects will then have no Screening Period.
- Run-in Period: The eCRF ‘Study Completion’ form will only be completed for subjects in the Treatment Period. Thus, if a subject is not eligible for treatment the Run-in Non-Completion is captured on the ‘Treatment Period Inclusion Criteria’ form.
- Follow-up Period: A Follow-up Period will be only available for subjects who did not roll over to CSL312_3002.

9 Study Population

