10.1 Analysis of Primary Endpoint

The primary endpoint is the time-normalized number of HAE attacks per month during the Treatment Period from Day 1 (first study drug administration) through Day 182 (inclusive).

Subjects will enter HAE symptoms into their eDiary, the start and end date and time, the interference of HAE symptom(s) with daily activities, and location(s) of the HAE symptom(s). Investigator-reported HAE attacks will be based upon review of subject diaries, relevant interval medical history, and physician judgment. The investigator may ask clarifying questions to assist in his/her assessment of whether or not an HAE attack occurred. If an attack occurred, then the investigator will record an attack in the eCRF form, the start/end date and time, the attack location(s), and the severity of the attack based on the most severe symptoms. For every visit, the investigator will report all HAE attacks that have occurred in the interim since the last visit the subject attended.

For all analyses considering HAE attacks, only the HAE attacks confirmed and reported by the investigator using the eCRF ‘HAE Attacks’ form will be used.

HAE attacks with a start date on or after the first day of the Run-in Period but prior to the date and time of the first study drug administration will be counted for the Run-in Period.

HAE attacks with a start date and time after the first study drug administration through Visit Day 182 (inclusive) or End of Study visit (whatever is first) will be counted for the Treatment Period and will be included in the analyses of efficacy.

The primary endpoint will be analyzed using the ITT and PP Analysis Set. The ITT Analysis Set will be used as the primary analysis and the PP Analysis Set will be used as the supplementary analysis (see [Section 10.1.3](#)).

The primary endpoint, time-normalized number of HAE attacks per month, is calculated per subject as:

$$[\text{the number of HAE attacks} / \text{length of subject treatment in days}] * 30.4375$$

where the length of subject treatment is calculated as:

$$[\text{the date of Study Visit Day 182 or the End of Study date [whatever is first]} - \text{the date of Study Visit Day 1 of the Treatment Period} + 1].$$

To transform the length of subject treatment which are calculated in days in years the number of days is divided by 365.25. Thus, time-normalized number of HAE attacks per year is calculated per subject as:

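### The Run-in attack rate counts attacks up to the first dose, but its length may stop at an undefined Run-in completion date; if that date is earlier, the affected subjects' baseline rates are too high

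*SAP*

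**What the plan says.** **Numerator.** SAP 10.1 assigns to the Run-in every attack that starts on or after its first day and "prior to the date and time of the first study drug administration will be counted for the Run-in Period".

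**Denominator.** SAP 10.3.2.1 divides that count by the length of the Run-in in days and multiplies by 30.4375. The length runs from the Run-in Day 1 visit to the Treatment Day 1 visit or the "Date of Run-in Completion/Non-completion [whichever is first".

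**Table 8 (SAP 8.3).** The Run-in row gives the End Date as "date of the Day 1 Visit of Treatment Period" and nothing else. The Duration column of the same row repeats the rule that takes the earlier date. SAP 8.3 says that these definitions supply the denominators of the time-normalized endpoints.

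**Completion date.** The technical note under Table 8 explains only the other half of the term: "if a subject is not eligible for treatment the Run-in Non-Completion is captured on the" Treatment Period inclusion form. For a subject who is randomized, the SAP does not say what the Run-in completion date is or where it is recorded.

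**Timing in the protocol.** Protocol 4.1.3 requires at least 1 month of Run-in. Protocol 8.7.3.3 adds: "Subjects should enter the Treatment Period no later than 15 days after the Day 60 telephone contact", with sponsor approval needed for later entry.

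**The concern.** The secondary efficacy analyses use the ITT set, so every subject in them was randomized. For such a subject the earlier-date rule can do one of two things. It has no effect when the two dates coincide, or it removes days from the denominator whose attacks are still counted. It can never lower the baseline rate, so any error runs one way.

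Attacks in such a gap would be captured. Protocol 8.7.3.3 closes diary access at Day 60 only for subjects who will not enter the Treatment Period, and the diary is reviewed again at the Treatment Day 1 visit (Protocol 8.7.4.1).

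The Run-in rate is used in these places:

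- the within-subject percentage reduction and the counts of subjects reaching 50%, 70% and 90% (SAP 10.3.2.1)
- their summaries for each 3-month half (SAP 10.3.3)
- the Japanese descriptive summary of the reduction (SAP 10.2)
- the continuous baseline covariate in the Poisson sensitivity model (SAP 10.1.2, which refers to 10.3.2.1)

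**Working it through.** **The plan's own figures.** The documents give no figure for the Run-in rate or its length, so there is none to reproduce. The stated power of about 90% for 24 + 16 subjects does reproduce (90.7% by the O'Brien-Castelloe method, 91.5% by simulation), but it does not depend on the Run-in rate.

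**Inputs.** L is the number of days from Run-in Day 1 to the recorded completion date, and g is the number of days from completion to the Treatment Day 1 visit. The SAP takes a plain difference of dates, so completion at the Day 60 contact gives L = 60 − 1 = 59 and completion at Day 30 gives L = 29. The only gap limit in the documents is the 15 days after the Day 60 contact. No gap is stated after a Day 30 exit. Completion on either day is an assumption.

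**Formulas.** With a constant attack rate:

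- Inflation factor: f = (L + g)/L
- Reported reduction for a true reduction r: 1 − (1 − r)/f
- True reduction that already meets the 50% cut: 1 − 0.5f

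| L | g | f | True 0% reported as | True 40% reported as | True 90% reported as | True reduction reaching the 50% cut |
|---|---|---|---|---|---|---|
| 59 | 0 | 1.000 | 0.0% | 40.0% | 90.0% | 50.0% |
| 59 | 7 | 1.119 | 10.6% | 46.4% | 91.1% | 44.1% |
| 59 | 15 | 1.254 | 20.3% | 52.2% | 92.0% | 37.3% |
| 29 | 7 (assumed) | 1.241 | 19.4% | 51.7% | 91.9% | 37.9% |

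For L = 59 and g = 15, f = 74/59 = 1.254 and 1 − 0.60/1.254 = 52.2%. A true 100% reduction stays at 100% for any f.

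**One subject, counted directly (L = 59, g = 15).**

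- Five attacks by completion and one in the gap: the SAP rate is 6/59 × 30.4375 = 3.10 per month. A matched window gives 6/74 × 30.4375 = 2.47 (to first dose) or 5/59 × 30.4375 = 2.58 (to completion).
- Five attacks and none in the gap: the SAP rate is 2.58, equal to the rate to completion. It is too high only against the rate to first dose, 5/74 × 30.4375 = 2.06.

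**With the plan's assumed treatment rates.** Take an illustrative baseline of 2.0 per month and f = 1.254. CSL312 at 0.3125 moves from 84.4% to 87.5%, and placebo at 1.3 moves from 35.0% to 48.2%. Neither crosses a responder cut. The change of class therefore concerns subjects close to a threshold.

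**Both arms together.** An illustrative simulation used 36 and 24 subjects, half with L = 29 and half with L = 59, gaps of 0 to 15 days after either exit, and a mean of about 3 attacks per month. These are assumptions, and the gaps after Day 30 have no source in the documents.

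- No treatment effect: the share of 50% responders rose from 10.5% with matched windows to 18.3% with the SAP rule, in both arms. The between-arm Wilcoxon test rejected in 4.3% and 4.1% of runs respectively, so no between-arm bias appeared.
- Treatment effect at the plan's rate ratio (0.3125/1.3): responders rose from 90.9% to 94.9% on CSL312 and from 10.4% to 18.0% on placebo. The difference between arms narrowed from about 81 to about 77 percentage points.

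**The case against.** The strongest reply is that the two dates coincide for anyone who is randomized. Protocol 8.7.3.3 says the Day 60 contact ends the Run-in for subjects who turn out not to be eligible. Footnote C of the Run-in schedule sends eligible subjects on to the Day 1 visit, and Protocol 4.1.3 and 8.7.3.2 treat leaving the Run-in and entering the Treatment Period as one step. On that reading, the 15 days simply lengthen the Run-in and are in the denominator. The completion/non-completion term would be there because Run-in failures have no Treatment Day 1, and the Table 8 End Date column fits this.

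Much of this stands. No passage shows a completion date before Treatment Day 1 for a randomized subject, so a gap is possible but not demonstrated.

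It does not dispose of the point. Run-in failures are not in the ITT set, so in SAP 10.3.2.1 the term has no such job. The rule as written applies to every subject, names completion as well as non-completion, and conflicts with the End Date column. A programmer who finds a completion date in the data would have to use it.

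Stronger readings that a reader might infer are not supported:

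- **All within-subject reductions are inflated.** Only subjects whose completion date precedes Treatment Day 1 are affected, and those attack-free on treatment stay at 100%.
- **The rate is inflated by half after a 30-day Run-in.** That carries the 15-day allowance over to a Day 30 exit, for which the documents state no gap.
- **The trial's conclusion is biased towards CSL312.** Any gap precedes the first blinded dose, so the baseline is affected alike in both arms. The primary endpoint, H02 (between-arm reduction in means) and H03 (attack-free in the first 3 months), as the SAP defines them, do not use the Run-in rate.

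**Conclusion.** The point holds as a defect in the stated rule. The counting window and the length do not match, Table 8 disagrees with itself, and the completion date is undefined for randomized subjects.

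The size depends on a fact that the documents do not settle. The factor is 1.00 if completion and Treatment Day 1 always coincide. It is about 1.25 for a subject taken as completing at the Day 60 contact and using the full 15 days, assuming a constant attack rate. In that case a true reduction of about 37% would already count as a 50% response.

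What is at risk is the reported size of within-subject reductions and responder percentages in both arms, and added noise in the Poisson covariate. The confirmatory results listed above are not at risk. The change is worth making before unblinding because any error goes one way and the remedy is simple.

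**What to change.** In SAP 8.3 (Table 8, Duration) and SAP 10.3.2.1, define the Run-in length for every randomized subject as the Treatment Day 1 visit date minus the Run-in Day 1 visit date. This matches the Table 8 End Date column and the counting rule in SAP 10.1. Keep the completion/non-completion date for Run-in failures only, and say so. The alternative is to stop the attack count at the same date as the length, but that discards observed days.

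The cost is a change of SAP wording. Both visit dates are already used by the SAP, and no new data are needed. If the dates always coincide, no result changes.

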4.5 Determination of the Sample Size

In total, 60 subjects are planned to be randomized.

Forty subjects with C1-INH HAE type 1 and type 2 completing the 6-month Treatment Period are needed to achieve a power of approximately 90% for a two-sided Wilcoxon Test (alpha of 5%). Subjects will be randomized to the Active Arm or the Placebo Arm with a ratio of 3:2. An attack rate per month of 0.3125 for CSL312-treated subjects and of 1.3 for subjects receiving placebo are assumed. The monthly attack rates of placebo and of CSL312 are assumed to be Poisson distributed.

The sample size calculation is performed with SAS 9.4 using proc power procedure with twosamplewilcoxon test=WMW which performs power analyses for the Wilcoxon-Test for two independent groups, i.e. the CSL312 and the Placebo treatment in Study CSL312_3001. The Wilcoxon Rank Sum test is testing from departure from the null hypothesis and is assessing if there is a location shift between the distributions of the HAE attack rates of the CSL312 and the Placebo treatment. SAS Proc Power procedure uses the O'Brien-Castelloe approach to compute approximate power. Alpha is set to 5% [O'Brien & Castelloe, 2006]. The assumed monthly attack rates of placebo and of CSL312 (i.e. 1.3 and 0.3125 attacks/month, respectively) are used as the two means of the two Poisson distributions. The randomization ratio of 3:2 was implemented by GROUPNS = (24 16) resulting in a total sample size of 40 which is the lowest one reaching 90% power.

It is targeted to randomize approximately 5 adolescents into the treatment period with a randomization ratio of 3:2 (active:placebo).

To allow for sufficient safety data, to increase the likelihood of adolescents entering the study and, to have at least 40 subjects reaching the end of the study, an additional 20 subjects are planned to be randomized.

In case it is not feasible to randomize the targeted number of adolescents, the targeted total sample size will be achieved by randomizing the needed number with adult subjects.

In addition, it is targeted to include 5 Japanese subjects into the total 60 subjects randomized.

Based on Method 1 and Method 2 in the [Basic principles on Global Clinical Trials] the sample size of the Japanese subjects are planned as below. The point estimate of the endpoint in each arm for Japanese population and other regions (for Method 2) are assumed as the same as that for the global population.

Method 1

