With setting the notations of treatment differences between CSL312 and placebo arm as D, the treatment difference in the global population as D_{all} , and the treatment difference in the Japanese subpopulation as D_{Japan} , the probabilities of $D_{Japan}/ D_{all} > 0.5$ were calculated for the settings that the global sample size is 60 patients (CSL312 arm = 36 patients, and placebo arm = 24 patients) including the Japanese sample size of 5 – 8. The Japanese sample sizes of each arm were rounded based on the 3:2 randomization ratio.

Table 4 Sample Size Justification for Japanese Subjects - Method 1

Japanese sample size			Probability (%) of $D_{Japan}/ D_{all} > 0.5$	
Total	CSL312	Placebo	With median	With mean
5	3	2	64	70
6	4	2	63	71
7	4	3	65	76
8	5	3	73	76

Method 2

With setting the notations of treatment differences between CSL312 and placebo arm as D, the treatment difference in the global population as D_{all} , the treatment difference in the Japanese subpopulation as D_{Japan} and the treatment difference in other regions x as $D_{other-x}$, the probabilities of that all of the global, Japan and other regions of $D > 0$ were calculated for the settings that the global sample size is 60 patients (CSL312 arm = 36 patients, and placebo arm = 24 patients), the Japanese sample size is 5 – 8, the sample size of North America and Europe are assumed to be the same. The sample sizes of each arm for Japan and other regions were rounded up based on 3:2 randomization ratio.

Table 5 Sample Size Justification for Japanese Subjects - Method 2

Sample size for each region			Probability (%) of all of D >0	
Japan	North America*	Europe*	With median	With mean
5	27	28	75	86
6	27	27	73	85
7	26	27	70	91
8	26	26	67	92

* Expected that the sample sizes for North America and Europe would be the same. If not divisible, the sample size of Europe includes one more patients than that of North America.

As the results, if the Japanese sample size is 8, the probabilities to achieve consistency between the Japanese subset and the global population are 67%–92% using mean and median with 3:2 randomization ratio based on Method 1 and 2. Eighty percent probability would be achieved with 5 Japanese patients already when using the mean and Method 2.

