8.1 Missing Data

Missing data occurs when any requested data are not provided, leading to blank fields on the collection instrument. These data will be indicated by the use of a “blank” in subject listing displays. Answers such as “Not applicable” and “Not evaluable” are not considered to be missing data and should be displayed as collected.

Only missing values for the primary efficacy endpoint (i.e., time-normalized number of HAE attacks) during Treatment Period will have an impact on the primary analyses of the comparison between CSL312 versus placebo. The time-normalized number of HAE attacks will be considered as missing for subjects who discontinued within 30 days after the first study drug administration.

The primary efficacy endpoint will be hardly missing due to the robust derivation rule (i.e., the normalization of the number of HAE attacks by time) and treatment policy strategy for the estimand. It is assumed that the outcomes for discontinued subjects are comparable to the outcomes for those who do not discontinue.

In the previous phase II study CSL312_2001 there was no pattern in the attacks under Placebo and CSL312 observed. It can be assumed from study CSL312_2001 that the attack rate for an observation period of > 30 days and < 6 months is comparable to the attack rate of ca. 6 months.

For secondary endpoints which are also based on the HAE attack rate the assumption above is subsequently also applicable.

The details of handling missing data are presented in the corresponding sections of this SAP for respective analyses (e.g., primary and secondary efficacy analyses, safety analyses).

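### Attack-free percentages credit subjects who leave early without an attack with the whole window: at 6 months this follows from the stated rules, and the wording of H03 permits it

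*SAP*

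**What the plan says.** SAP Section 10.3.2.1 plans three attack-free analyses on the ITT set.

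- **6 months.** A subject is attack-free if the reduction from run-in in the time-normalized rate is 100%. The rate is taken from Section 10.1. Sections 10.1 and 10.1.1 compute it on the days actually observed for anyone with at least 30 days, and 10.1.1 treats the result for a later leaver as measured, not missing.
- **First 3 months (H03).** The outcome is "The number and percentage of subjects who do not experience a HAE attack in the first 3 months after first study drug administration", compared by a Fisher test. No minimum observation time and no rule for early leavers is given. Under Section 10.5, H03 is third in the hierarchy and must be rejected before H04 is tested.
- **Second 3 months.** "The same analysis will be repeated for the second 3 months after first study drug administration".

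Section 8.1 assumes that an attack rate observed for more than 30 days is comparable to one observed for about 6 months, and adds: "For secondary endpoints which are also based on the HAE attack rate the assumption above is subsequently also applicable". Section 8.1.1 bases percentages on subjects with non-missing values. Section 10.3.1 defines no secondary estimand, and the missing-value sensitivity analysis in Section 10.1.2 covers the primary endpoint only.

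**The concern.** A constant attack rate can justify dividing by a shorter observation time. It cannot justify calling a subject event-free for a period in which the subject was not observed. Even at a constant rate, the chance of having had no attack is much higher at Day 31 than at Day 91 or Day 182. Counting attack-free leavers as successes therefore pushes the percentage up in both arms, and more in the arm with more leavers.

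The SAP's own analyses would also disagree about the same person. The planned Kaplan-Meier analysis of time to first attack censors such a subject at the End of Study visit, while Section 10.3.2.1 makes the subject a 6-month success.

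At stake are the attack-free percentages, which readers will take as the share of patients with no attack over 3 or 6 months, and a clear outcome definition for a hypothesis inside the alpha-controlled hierarchy.

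**Working it through.** **Inputs (SAP Section 4.5).** "An attack rate per month of 0.3125 for CSL312-treated subjects and of 1.3 for subjects receiving placebo are assumed". Attack counts in both arms are taken as Poisson. Planned randomization is 36 CSL312 and 24 placebo. No dropout rate is given. I assume 5% to 33%; the upper end is 20/60, the loss that would still leave 40 completers.

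**The plan's own figure.** "The randomization ratio of 3:2 was implemented by GROUPNS = (24 16) resulting in a total sample size of 40", for about 90% power. With Poisson means 0.3125 and 1.3, the probability that a placebo count exceeds a CSL312 count (ties counted half) is 0.7673, so the odds are 0.7673/0.2327 = 3.298. The O'Brien-Castelloe method then gives power 0.907, so the plan's figure is reproduced. The SAP states no attack-free percentage and no power for H03.

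**One subject traced through the 6-month rule.** The subject leaves at Day 31 with no attack. The rate is (0/31) × 30.4375 = 0. The reduction is 100 × [1 − 0/run-in rate] = 100%. The subject is attack-free for 6 months.

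**Probability of no attack by day t** = exp(−rate × t/30.4375):

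| | Day 31 | Day 91 | Day 182 |
|---|---|---|---|
| CSL312 | 72.7% | 39.3% | 15.4% |
| Placebo | 26.6% | 2.1% | 0.04% |

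**Leavers.** Let exits be uniform from Day 30 to the end of the window T, and write k = rate/30.4375. The average chance that a leaver exits attack-free is [exp(−30k) − exp(−kT)] / [k(T − 30)]. For CSL312 this is 54.6% (T = 91) and 37.2% (T = 182); for placebo it is 9.9% and 4.3%.

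**Reported percentage** if a share d leaves within the window and attack-free leavers count as successes: (1 − d) × full-window value + d × leaver value. Example, CSL312 at 6 months with d = 20%: 0.8 × 15.4 + 0.2 × 37.2 = 19.8%.

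| d | 3 months, CSL312 / placebo | 6 months, CSL312 / placebo | 3 months, leavers as failures |
|---|---|---|---|
| 0 | 39.3% / 2.1% | 15.4% / 0.04% | 39.3% / 2.1% |
| 5% | 40.1% / 2.4% | 16.5% / 0.3% | 37.3% / 2.0% |
| 10% | 40.8% / 2.8% | 17.6% / 0.5% | 35.4% / 1.8% |
| 20% | 42.4% / 3.6% | 19.8% / 0.9% | 31.4% / 1.6% |
| 33% | 44.4% / 4.7% | 22.7% / 1.5% | 26.2% / 1.4% |

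In the 3-month columns d is the share gone by Day 91, so the last row is severe. If one third left evenly over Days 30 to 182, only 33.3% × 61/152 = 13.4% would be gone by Day 91, and the CSL312 inflation would be 0.134 × (54.6 − 39.3) = 2.0 points. One subject moves a percentage by 100/36 = 2.8 points on CSL312 or 100/24 = 4.2 points on placebo.

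**Effect on the H03 test (exact Fisher, 36 v 24).**

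- Power is 0.972 with no dropout. At 20% it is 0.961 with leavers counted as successes and 0.900 with leavers as failures; at 33% it is 0.958 and 0.782.
- Type I error: with equal true rates of 0.3125, rejection is 3.3% with no leavers, 3.8% with 20% leaving on CSL312 only and 4.7% with 33%. It also stayed below 5% at equal rates of 0.8 and 1.3.
- These results rest on even exits. If every leaver goes at Day 31, on CSL312 only, the CSL312 probability at rate 0.3125 is 0.8 × 39.3 + 0.2 × 72.7 = 46.0% against 39.3%, and the same calculation gives 5.7% rejection. With one third leaving it is 50.4% against 39.3%, and 10.1%. That is the most extreme timing the 30-day rule allows.

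**The case against.** The strongest reply has five parts.

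1. *H03 does not say that leavers count as attack-free.* Correct. The SAP is silent on this and on whether the 30-day minimum applies. For H03 the defect is an undefined outcome that permits the counting.
2. *Subjects with under 30 days are not successes at 6 months.* Correct: they have no rate and drop out of the percentage under Section 8.1.1.
3. *Second 3 months.* A reader might infer that someone gone before Day 91 is a success there even after earlier attacks. The documents do not support that as the rule. The Technical Note in Section 10.3.2.4 gives such a subject no rate for that period, and Section 8.1.1 keeps only non-missing values. What remains is that Section 10.3.2.1 does not repeat the exclusion, in an analysis outside the hierarchy.
4. *The test is hardly affected.* A reader might infer that H03, and through it H04, has an inflated false-positive rate. With even exits it does not. An excess needs many one-sided exits clustered just after Day 30, and no dropout rate or timing in the documents points to that. With 20% dropout in both arms, the arm difference moves only from 37.2 to 38.7 points.
5. *Kaplan-Meier curves are already planned, and failure imputation overcorrects.* Both stand. The curves handle leavers properly but are not the H03 test or the reported percentages. At 20% dropout, counting leavers as failures gives 31.4% against a full-window 39.3%, a larger error than the 42.4% obtained by counting them as successes.

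**Conclusion.** The concern holds in a limited form. For the 6-month endpoint, the stated rules report a subject who leaves after Day 30 without an attack as attack-free for 6 months, and Section 8.1 does not justify this. For H03, the wording allows the same counting.

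At the planning rates the CSL312 percentage is inflated by 1.1 to 7.3 points at 6 months and 0.8 to 5.1 points at 3 months; placebo by 0.2 to 1.4 and 0.4 to 2.6 points. This assumes a constant Poisson rate, dropout unrelated to attacks, exits spread evenly from Day 30, and 5% to 33% leaving within the window. The 33% is an outer bound, since SAP Section 4.5 gives safety data and adolescent enrolment as further reasons for the extra 20 subjects.

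The main harm is to the reported percentages. The primary analysis is not affected. The rule should be settled before unblinding.

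**What to change.** In SAP Section 10.3.2.1, state that:

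- a subject is attack-free in a window only if no attack was recorded in it and the subject was observed through the Day 91 or Day 182 visit, allowing the ±4-day visit window so that a compliant subject seen at Day 178 is not failed;
- all other ITT subjects, including those with under 30 days, count as not attack-free in the Fisher test;
- subjects who left before Day 91 are not attack-free successes in the second 3 months, in line with the Technical Note in Section 10.3.2.4;
- the cut-off at last dose plus 30 days in Section 10.1.1 does not make a subject with a later recorded attack in the window attack-free.

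Report the Kaplan-Meier attack-free proportions at Day 91 and Day 182, with 95% CIs, beside the percentages. If leavers are comparable to completers, as Section 8.1 assumes, this estimate is neither inflated nor deflated by leavers.

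The cost is a few sentences and no new data. The reported percentages fall, and H03 loses power if many leave by Day 91: about 0.96 to 0.90 at 20% dropout and 0.96 to 0.78 at 33%.
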